Study Protocol and Statistical Analysis Plan (SAP)

Official Title: Smartphone-based Mindfulness Training for Health Following Early Life Adversity

(Brief Title: Remote Mindfulness Training Following Early Life Adversity)

ClinicalTrials.gov ID (NCT number): NCT05516108

Protocol Date: 08/18/2022

Study Purpose

Early life adversity (ELA) confers potential lifelong health complications, and interventions are needed to mitigate risk. Mindfulness-based interventions (MBIs) have shown promise for improving mental health outcomes among adults exposed to childhood trauma, but whether MBIs can offset physical health risk is unknown. This two-arm, parallel-group, randomized trial aims to investigate the feasibility and acceptability of remote mindfulness and coping interventions among emerging adults who recall a history of childhood trauma with the goal to inform an efficacy trial examining stress-related health outcomes.

Overview

Adults with a history of ELA will be recruited (n=80). Participants will one week of baseline ambulatory stress ratings (5x daily), continuous mobile sensor data (e.g., heart rate, activity, and location from wearable devices and smartphones), and blood samples to assess inflammatory biomarkers (e.g., IL-6, CRP, TNF-a, IL-8, IL-10). Participants will then be randomly assigned to a 14-lesson smartphone-based (a) mindfulness intervention or (b) structurally matched active control intervention that trains common coping skills, both boosted with practice prompts randomly delivered throughout the day to permit retrospective evaluation of JIT prompts. Ambulatory and sensor data will again be collected during the intervention and for one week at post-intervention and one-month follow-up, and inflammatory biomarkers will be assessed at post-intervention and follow-up. Participants will be surveyed about the acceptability of mobile data collection and intervention delivery.

Study Objectives

This trial aims to evaluate the feasibility, acceptability, and preliminary effects of smartphone-based mindfulness and control interventions among emerging and young adults with a history of ELA. Two primary hypotheses will be tested:

- The interventions and assessments will meet feasibility and acceptability benchmarks in this sample, including recruitment targets, safe implementation, and intervention/assessment adherence and fatigue.
- Mindfulness training is expected to reduce daily life stress, normalize stress biology, and reduce markers of inflammation from pre-intervention to post-intervention and one-month follow-up.

Exploratory aims involve (1) developing machine learning models to estimate daily life stress from passive sensor data and (2) using these models to inform future JIT intervention.

Methods

Participants:

80 participants will be recruited. English-speaking adults (ages 18-29 years) who report moderate-to-severe physical, emotional, or sexual abuse in childhood (based on Childhood

[figure not shown]
Trauma Questionnaire thresholds) and own data-enabled Android or iOS smartphones will be recruited in Pittsburgh. Those with severe mental health diagnoses (e.g., psychosis) will be excluded for safety. The sample is expected to be 65% white, 30% black, 5% other race; 5% Hispanic; and 50% female.

Recruitment:

Participants will be recruited for a study testing smartphone stress reduction programs, primarily through The University of Pittsburgh Pitt+Me research registry has nearly 30,000 potential participants ages 18-29. Interested participants will be pre-screened online for preliminary eligibility, then invited for an in-person baseline eligibility screening and visit.

Procedures:

Data will be collected across an 8-week study period as follows:

Lab visits include blood draw and questionnaire assessments. Ecological Momentary Assessment (EMA) includes surveys delivered at four random times daily and end-of-day diary assessments. Mobile sensor data collection includes AWARE phone sensor and Fitbit data.

T1: Baseline. Participants will attend a study visit to confirm eligibility, provide informed consent, complete psychosocial assessments, and prepare for the at-home assessments and intervention. Dried blood spot (DBS) samples will be collected to assess inflammatory biomarkers. During a one-week ambulatory stress assessment, participants will provide four ecological momentary assessments (EMA) and one evening diary survey daily assessing stress and resilience; stress physiology (HR) and activity (e.g., steps, sleep) via wearable device; and smartphone sensor data.

T2: Two-week intervention. Following baseline assessments, participants will be randomly assigned to the mindfulness intervention or coping control intervention condition. Participants will complete one 20-minute audio-guided lesson each day, plus receive 3 brief text-based practice prompts daily at random times. The interventions were developed by [name] and [name] and are matched on attentional demand, lesson length and structure, and voice. Interventions will be delivered via smartphone app that securely tracks participant activity, including timestamps at lesson and practice prompt start/completion and daily survey responses (stress assessments pre- and post-lesson, pre- and post-practice prompt, and each evening; practice prompt receptivity). This data will be integrated with phone sensor and wearable data to inform future JIT intervention tailoring. Staff will check in with participants on intervention days 3, 9, and 14 to provide support and monitor for adverse events.

Mindfulness intervention: Based on [name]'s Unified Mindfulness system, lessons train meditation techniques for 3 mindfulness skills: (1) concentration, a stable attention on present-moment body experiences; (2) sensory clarity, the detection and discrimination of sensory experiences; and (3) equanimity, an attitude of acceptance and receptivity toward present-moment experiences. Practice prompts build on the skills trained in each lesson, encouraging participants to practice brief moments of mindful awareness, mindfulness while doing daily tasks, or formal meditation for 5-10 minutes.

Coping control intervention: To parallel the structure of the mindfulness intervention without training present-moment attention or acceptance skills, participants are instructed to: (1) reflect and mind wander; (2) reappraise past and future events; and (3) analyze and solve personal problems. Practice prompts encourage participants to take brief mind-wandering breaks, apply reappraisal or problem-solving skills, or reflect for 5-10 minutes. This program controls for nonspecific effects (e.g., goals, daily practice, and treatment expectancies). Here, an active control program will inform the feasibility of the RCT design for future trials and will preempt differential dropout issues that are commonly seen in studies using no-treatment control groups.

T3: Post-intervention. Immediately following the intervention, participants will complete a one-week ambulatory stress assessment, including mobile sensor data collection, a psychosocial assessment in the lab, including qualitative program evaluations, and a blood draw to assess inflammatory biomarkers as at T1.

T4: Continued mobile sensor monitoring. Continuous sensor data and weekly self-reported intervention practice will be collected during a post-intervention three-week monitoring period.

T5: One-month follow-up. As at T1 and T3, participants will complete a one-week ambulatory stress assessment and return to the lab for a psychosocial assessment and blood draw. Participants will be debriefed and offered access to the interventions. Outcome assessors will be blind to condition during the trial.

Measures:

Participants will complete the following questionnaires in-person at pre-intervention (Visit 1), post-intervention (Visit 2), and one-month follow-up (Visit 3):

1. Demographics and health status data (e.g., age, sex, race, ethnicity, BMI, health status) (Visit 1 only)
2. Early Life Adversity, including Childhood Trauma Questionnaire, childhood emotional neglect, SES (via parent education and food insecurity), and domestic violence (Visit 1 only)
3. Treatment Expectancy-Credibility Questionnaire
4. Pittsburgh Sleep Quality Index
5. Perceived Stress Scale
6. Five Facet Mindfulness Questionnaire
7. Acceptance and Action Questionnaire – II

8. PROMIS Anxiety
9. PROMIS Depression
10. PROMIS Positive Affect
11. PROMIS Social Isolation
12. PROMIS General Self Efficacy
13. PROMIS General Life Satisfaction
14. Distress Tolerance Scale
15. Post Traumatic Stress Disorder Checklist
16. Cambridge Depersonalization Scale
17. Self Compassion Scale
18. Everyday Discrimination Scale (Visit 1 only)
19. Adverse Effects Survey (Visit 2, Visit 3 only)
20. Study Burden (Visit 3 only)

The following outcomes will also be collected:

1. *Ambulatory Stress Assessments*, delivered to participants' smartphones at T1, T3, and T5, will assess (1) EMA stress (state stress perceptions, stress events) and resilience (state positive/negative affect, social interactions) four times daily during between 8am and 8pm, and (2) average daily life stress via diary (stress perceptions, stress events), resilience (positive/negative emotions, social interactions), and intervention practice (T3, T5 only). At T2, participants will complete stress surveys before and after each intervention lesson, before and after each JIT prompt, and each evening, which will inform adherence and JIT prompt timing.
2. *Ambulatory Physiology*, tracked and stored via Fitbit wearable device throughout T1-T5, will include continuous HR data (via photoplethysmography) to pair with EMA stress surveys. Physiological data and continuous physical activity (via pedometer) and sleep (via actigraphy) data will be integrated daily into the AWARE database and will be used in machine learning analyses with passive sensor data to evaluate predictive models of state stress in daily life.
3. *Smartphone Passive Sensor Data* will be collected throughout T1-T5. The open-source AWARE application will be installed on participants' Android or iOS smartphones to continuously and unobtrusively collect data characterizing behavioral and contextual features. Sensor data will include device usage, location, movement, activity, noise, conversation, and communication; these features will be used to predict stress.
4. *Inflammatory biomarkers* will be quantified in batch from DBS samples collected at T1, T3, and T5. Pro-inflammatory cytokine IL-6 will be assessed using R&D's Ella Automated Immunoassay System. A larger panel of pro- and anti-inflammatory markers (e.g., TNF, CRP, IL-8, IL-10) will be assessed via multiplex with additional funding.

Eligibility Criteria:

Inclusion Criteria:

1. Emerging adults between 18 and 29 years old
2. English speaking
3. History of adverse childhood experiences (specifically, moderate-to-severe physical, emotional, or sexual abuse in childhood: scoring >9, >12, or >7 on respective

Childhood Trauma Questionnaire subscales 1)

4. Data-enabled Android or iOS smartphone
5. Able to meet study requirements

Exclusion Criteria:

1. Self-reported diagnosis of chronic physical disease (e.g., cancer, HIV, heart disease, diabetes, bleeding disorder)
2. Self-reported diagnosis of chronic mental disorder (e.g., schizophrenia, personality disorder, or psychotic illness) major neurological disorder, or suicidal thoughts or wishes at baseline
3. Medication use that interferes with HPA-axis activity (e.g., corticosteroids) or autonomic activity (e.g., antihypertensive medication)
4. Current antibiotic, antiviral, or antimicrobial treatment
5. Shift workers
6. Pregnancy or breastfeeding
7. Excessive alcohol use
8. Frequent illicit drug use
9. Regular systematic mind-body practice (>2 times per week)

Statistical Analysis Plan (SAP)

Power:

Sample size balances rules of thumb for pilot trial sample size (which range from 25-35 participants per treatment arm estimating a small between-group effect size, with larger pilot trials more accurately estimating variance and allowing for smaller sample sizes in efficacy trials) with calculations to detect medium within-group effects of mindfulness on EMA stress ($d=.40$). Therefore, we plan to enroll 80 participants (40 per condition).

Statistical Analysis Plan:

This study will evaluate two primary aims and one exploratory aim:

Aim 1 evaluates the feasibility and acceptability of the interventions and assessments, with the prediction that interventions and assessments will meet feasibility and acceptability benchmarks in this ELA sample, and mindfulness and control groups will show equivalence on these measures.

- Planned analysis: Feasibility and acceptability will be evaluated by comparing screening and enrollment numbers, participant retention, adherence to intervention and assessment protocols, treatment expectancies, intervention fatigue, and prompt timing to proposed benchmarks for success. Specifically, minimum feasibility benchmark ranges are as follows: 10% of those screened will be eligible; 60-70% of eligible participants will enroll; <10% of participants will show increases in daily stress, a measure of safe implementation; 80-90% of enrolled participants will be retained through the intervention period and 75-85% through the follow-up assessment period; participants will complete 85-95% of the intervention lessons, 60-70% of practice prompts, 75-90% of ambulatory assessments, and provide mobile sensor data on >75% of days. ANOVAs will test for equivalence of mindfulness vs. control groups on

feasibility and acceptability outcomes.

Aim 2 tests for mindfulness intervention changes to establish effect sizes for a future RCT, with the prediction that mindfulness training will reduce daily life stress, normalize stress biology, and reduce markers of inflammation from pre-intervention to post-intervention and one-month follow-up.

- Planned analysis: MLMs will be used to test for mindfulness intervention changes in daily life subjective stress events and perceptions, stress-related HR in daily life (HR during high stress surveys relative to average person-centered HR), and markers of inflammation from pre-intervention to post-intervention and one-month follow-up. Secondary MLM analyses will test for mindfulness intervention changes in daily life resilience (positive/negative affect; social factors) and daily life HRV. Tertiary MLM analyses will test for between-group differences (mindfulness vs. coping intervention) on all outcomes.

Exploratory aims involve developing machine learning models to estimate daily life stress from passive sensor data and lay the groundwork for future JIT intervention. First, machine learning models developed to estimate daily life stress from passive sensor data aim to have at least 80% accuracy and 70% recall. We will use the open-source RAPIDS pipeline to extract aggregated behavioral features. We will approach stress detection as a binary classification problem where each interval prior to a random EMA is assigned a value of 0 (low stress) or 1 (high stress) based on perceived stress rating and sensor features from that interval are used to predict class membership. We will use the RAPIDS pipeline to evaluate different cross-validation approaches (e.g., leave-one-out) as well as different machine learning algorithms (e.g., random forests, extreme gradient boosting machines). Methods will be evaluated in an iterative and exploratory manner to determine which yields the best performance with regard to accuracy and interpretability. We will examine overall accuracy, precision (i.e., positive predictive value), recall (i.e., sensitivity), and area under the receiver operating characteristic curve (AUROC) in evaluating model performance. Second, MLMs will test whether mindfulness practice prompts delivered at high stress times (operationalized as being ≥ 1 SD above the person-centered stress mean) reduce state stress and end-of-day stress each day during the intervention. These exploratory analyses will inform the design and implementation of a tailored JIT intervention in a future trial.

Finally, analyses will be run separately by sex to examine potential patterns hidden in pooled analyses.

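### Treatment expectancy is rated before assignment and then only after the programme ends, so the predicted arm equivalence on expectancy has no clean measure

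*Combined protocol and SAP*

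**What the plan says.** **Schedule of the questionnaire.** The Measures section opens with "Participants will complete the following questionnaires in-person at pre-intervention (Visit 1), post-intervention (Visit 2), and one-month follow-up (Visit 3"). The third item is the "Treatment Expectancy-Credibility Questionnaire". Items 1, 2, 18, 19 and 20 carry a visit restriction and this one does not, so it is given at Visits 1, 2 and 3.

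**Assignment.** Under Procedures, T1, "Participants will attend a study visit to confirm eligibility, provide informed consent, complete psychosocial assessments, and prepare for the at-home assessments and intervention". Under T2, "Following baseline assessments, participants will be randomly assigned to the mindfulness intervention or coping control intervention condition". The Overview gives the same order: after the baseline week, "Participants will then be randomly assigned to a 14-lesson smartphone-based" programme.

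**Visit 2.** Under T3, "Immediately following the intervention, participants will complete a one-week ambulatory stress assessment, including mobile sensor data collection, a psychosocial assessment in the lab".

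**Use made of expectancy.** The description of the coping control says "This program controls for nonspecific effects (e.g., goals, daily practice, and treatment expectancies"). In the SAP, Aim 1 compares "treatment expectancies, intervention fatigue, and prompt timing to proposed benchmarks for success", predicts that the two groups will be equivalent on the feasibility and acceptability measures, and assigns that question to ANOVAs. It names no visit and no equivalence margin.

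**The concern.** An active control answers the objection that one programme simply raised higher hopes than the other. Checking this requires a rating of the programme the participant has actually been given, taken before its effects can colour the answer. None of the three scheduled administrations meets both conditions.

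What is at stake is a stated purpose of the control and one of the Aim 1 measures. The pilot is meant to tell a later efficacy trial whether this control design works, and expectancy matching is part of that. An early rating that is not collected cannot be recovered afterwards.

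**Working it through.** The plan states no figure to reproduce. The check is one of timing, followed by calculations of what each rating can show.

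**Step 1: timeline.**

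| Point | Assigned programme known? | Benefit possible? | Expectancy rated? |
|---|---|---|---|
| Visit 1 (T1) | No | No | Yes |
| Assignment, then lesson 1 (T2) | Yes | Barely | No |
| Rest of T2: app surveys on stress and prompt receptivity; staff contacts on days 3, 9 and 14 for support and adverse events | Yes | Yes | None listed |
| Visit 2 (T3) | Yes | Yes, after 14 lessons | Yes |
| Visit 3 (T5) | Yes | Yes | Yes |

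The only row where the programme is known and benefit has barely begun has no rating.

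**Step 2: Visit 1 comparison.** Both arms answer before assignment, so any difference between them is chance. A simulation of a two-sided 5% two-group test on such a score (40 per arm, 20,000 runs) rejected in 0.050, 0.050 and 0.048 of runs when the gap arising later was set at 0.5, 0.8 and 1.0 SD. This follows by construction, because a score taken before assignment cannot depend on a gap that assignment creates.

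**Step 3: a rating taken after assignment.** Power = Φ(Δ/√(2/n) − 1.96), with n = 40 per arm (SAP, Power) and √(2/40) = 0.2236. The gaps are assumptions, since the documents give none.

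- Δ = 0.5: Φ(2.236 − 1.96) = 0.61
- Δ = 0.8: Φ(3.578 − 1.96) = 0.95
- Δ = 1.0: Φ(4.472 − 1.96) = 0.99

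**Step 4: what Visits 2 and 3 mix in.** Suppose the arms start equal in expectancy. The gap induced by benefit alone is (correlation of rating with benefit) × (arm difference in benefit). Both inputs are assumptions.

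- Correlation 0.3 to 0.5, benefit difference 0.4 SD: 0.3 × 0.4 = 0.12 to 0.5 × 0.4 = 0.20 SD
- Wider range, correlation 0.3 to 0.7, benefit difference 0.2 to 0.5 SD: 0.3 × 0.2 = 0.06 to 0.7 × 0.5 = 0.35 SD

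The product treats the whole correlation as benefit driving the rating, so it is an upper bound for given inputs. The effect can also conceal a gap: if the control started 0.20 SD ahead and benefit added 0.20 SD to the mindfulness ratings, Visit 2 would show no difference.

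**Step 5: who answers, and how precisely.** At the SAP retention benchmarks, 80–90% of 40 is 32–36 per arm after the intervention, and 75–85% is 30–34 at follow-up (equal loss in both arms assumed). The 95% half-width for an arm difference is 1.96 × √(2/n) SD:

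- n = 40: 1.96 × 0.2236 = 0.44
- n = 36: 1.96 × 0.2357 = 0.46
- n = 32: 1.96 × 0.25 = 0.49

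**Step 6: equivalence.** A non-significant ANOVA does not show equivalence at any visit. Even if the true difference is zero, two one-sided tests at 5% each reach 80% power only for a margin of (1.645 + 1.282) × 0.2236 = 0.65 SD with 40 per arm.

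**The case against.** The strongest reply is that Visits 2 and 3 are post-assignment ratings, and the instrument covers credibility, which can properly be rated after exposure. The assumed contamination of 0.12–0.20 SD is less than half the 0.46–0.49 SD half-width at Visit 2, and contamination of that size could not by itself produce a gap of 0.5–1.0 SD. This stands: those ratings are useful as description. They still cannot separate what participants expected from what they experienced.

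A second reply is that the SAP names no visit, so the only defect is an unspecified time point. This does not stand, because none of the existing visits supplies the missing rating.

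A third is that the control's claim rests on design: both programmes are recruited for as smartphone stress reduction, and they are matched on attentional demand, lesson length, structure and voice. That makes matching plausible. It does not measure it, and Aim 1 proposes to test it.

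A reader might also infer that unequal expectancy is the main rival explanation for the Aim 2 results, on the view that nearly all of them are self-reported. The documents do not support this. Aim 2 also includes stress-related heart rate, heart rate variability and inflammatory markers. Its primary tests concern change within the mindfulness arm, where matching between arms rules nothing out, and between-group tests are tertiary.

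**Conclusion.** The point holds in a limited form. The plan has no clean measure for its predicted arm equivalence on treatment expectancies, or for its statement that the control handles them. Visit 1 is uninformative about the assigned programme. Visits 2 and 3 give some information on credibility, but it is mixed with experienced benefit and limited to retained participants.

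The scope is the Aim 1 arm comparison and the tertiary between-group tests, mainly for self-reported stress and affect. The primary within-group tests are unaffected. It would go too far to say that the trial learns nothing about expectancy.

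The timing finding rests on the documents alone. The gap sizes, correlations and benefit differences are assumptions and serve only to show scale. For a feasibility pilot the consequence is moderate, but the correction is cheap and worth making before enrolment.

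**What to change.** - Give the existing questionnaire once in the intervention app, after assignment and around lesson 1, and name that administration in the Measures section and the SAP as the time point for the between-arm expectancy comparison.
- Keep Visit 1 as baseline and Visits 2 and 3 as descriptive post-exposure ratings. Visit 3 need not be dropped.
- Report the arm difference with its confidence interval, and state that a non-significant ANOVA will not be read as equivalence. Any equivalence claim would need a margin set in advance, and at this sample size only a wide one could be supported.

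The app already delivers surveys before and after each lesson, so the cost is one short form, a line in each section, and a few minutes of participant time on day 1. Two small limits remain: a rating taken after lesson 1 follows slight exposure, and anyone who never opens the app would be missing, so the 40-per-arm figures assume that everyone responds.

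### The only listed self-report of study burden is given at the one-month follow-up, so it leaves out everyone lost before then, including any who left because of burden

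*Combined protocol and SAP*

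**What the plan says.** In the combined protocol and SAP, the Measures section sets questionnaires "in-person at pre-intervention (Visit 1), post-intervention (Visit 2), and one-month follow-up (Visit 3". Item 20, the last, is "Study Burden (Visit 3 only". Item 19, the Adverse Effects Survey, is given at both Visit 2 and Visit 3. No questionnaire on leaving the study is described.

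The Overview states: "Participants will be surveyed about the acceptability of mobile data collection and intervention delivery". It gives no time point and does not say whether this survey is the Study Burden form. At T3 (Procedures) there are qualitative evaluations, described as being of the program.

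The Aim 1 planned analysis compares screening and enrollment numbers, "participant retention, adherence to intervention and assessment protocols, treatment expectancies, intervention fatigue, and prompt timing to proposed benchmarks for success". The retention benchmark reads "80-90% of enrolled participants will be retained through the intervention period and 75-85% through the follow-up assessment period". The benchmarks for the assessments themselves are "75-90% of ambulatory assessments, and provide mobile sensor data on >75% of days". Study Burden is not named in this analysis and has no benchmark. The Power section gives the sample size: "we plan to enroll 80 participants (40 per condition".

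**The concern.** The study asks a lot of participants: an eight-week period with five surveys a day in three separate weeks, more during the intervention, continuous phone and wearable sensing, and three blood samples. Whether people find that tolerable is part of what a feasibility trial should learn. A burden rating taken only at the final visit comes from those who tolerated the study long enough to reach it. If burden is one reason for leaving, the rating will look better than it would among all enrolled.

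The behavioural measures do not fill this gap. A participant who stops because of survey load looks the same in the retention and completion figures as one who moved away, lost interest or became distressed. A sponsor deciding what to trim in a later trial would want to tell these apart.

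Timing adds to the problem. The survey load peaks during the two-week intervention, and Visit 3 comes about four weeks or more after that period ends.

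**Working it through.** No formula in the plan produces this point, and the sample size does not depend on it. The check covers who can answer the form, what their answers can say about all enrolled, and when they are asked.

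**Inputs from the document**
- Enrollment: 80, 40 per arm (Power).
- Retention benchmarks: 80-90% through the intervention, 75-85% through follow-up (Aim 1 planned analysis).
- Burden form at Visit 3 only (Measures, item 20).

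**Assumptions**
- Retention through follow-up stands for attendance at Visit 3.
- Retention through the intervention stands for attendance at Visit 2.
- Actual retention falls within the benchmark ranges. These are minimum targets, so it could fall outside them.

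**1. Who can answer (80 × retention)**

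| Form given at | Retention | Can answer | Cannot answer | Per arm, if loss is equal |
|---|---|---|---|---|
| Visit 3 (as planned) | 75% | 80 × 0.75 = 60 | 20 | 30 |
| Visit 3 (as planned) | 85% | 80 × 0.85 = 68 | 12 | 34 |
| Visit 2 (if added) | 80% | 80 × 0.80 = 64 | 16 | 32 |
| Visit 2 (if added) | 90% | 80 × 0.90 = 72 | 8 | 36 |

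Adding Visit 2 gains 64 − 60 = 4 respondents at the low end and 72 − 68 = 4 at the high end, or 5 percentage points. It leaves 8-16 people without a rating, and only a form sent at withdrawal can reach them.

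**2. What the respondents' figure says about all enrolled**

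Let *r* be the share responding and *p* the share of respondents who rate burden acceptable. Among all enrolled, the acceptable share lies between *r·p* (no non-responder finds it acceptable) and *r·p* + (1 − *r*) (all do). The document gives no value for *p* and no cut-off for acceptable, so the values below are illustrations.

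| Assumed *p* | *r* = 0.75 | *r* = 0.85 |
|---|---|---|
| 0.80 | 0.60 to 0.85 | 0.68 to 0.83 |
| 0.90 | 0.675 to 0.925 | 0.765 to 0.915 |

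The width of each range is 1 − *r*, whatever *p* is: 25 points at 75% retention and 15 points at 85%. That width depends only on the plan's benchmarks.

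A milder scenario, also assumed, has 20% of completers rating burden unacceptable and leavers twice as likely to do so. The figure for all enrolled is then 0.75 × 0.20 + 0.25 × 0.40 = 25%, or 0.85 × 0.20 + 0.15 × 0.40 = 23%. That is a shift of only 3-5 points.

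**3. When they are asked**

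- T1, T3 and T5 weeks: 4 momentary surveys + 1 evening diary = 5 a day.
- T2: before and after one lesson (2), before and after each of three prompts (6), and one in the evening (1) = 9 a day if all are completed.
- T3 (one week) and T4 (three weeks) lie between the end of T2 and the start of T5, so the Visit 3 rating comes about four weeks or more after the heaviest survey load.

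**The case against.** A reader might infer that the acceptability of the assessments is judged solely by those who stayed. The document does not support that. Retention is stated for enrolled participants, so every leaver counts against it. Completion of ambulatory assessments and days with sensor data are collected from T1 onward, so people who later leave contribute while they take part. The document does not say whether the adherence denominators are all enrolled or only those retained, but retention alone rules out the stronger reading.

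A reader might also infer that a completer-only burden score would bias the Aim 1 verdict. No stated success criterion depends on that score: it has no benchmark and is not named in the planned analysis. Nor does the document say that the score will set the assessment load of a later trial. It says only that the trial is meant to inform one.

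Other feedback is collected before Visit 3: prompt receptivity during T2, staff contact on intervention days 3, 9 and 14, and program evaluations at T3. Intervention fatigue is listed in Aim 1, though with no named instrument. The acceptability survey in the Overview might be given earlier or be a separate form. These soften the point without removing it. The staff contacts are for support and adverse events, the T3 evaluations are not described as covering the assessments, and the Overview survey has no stated timing.

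The best argument for the present schedule is that a rating of the whole study needs exposure to the whole study. At Visit 2 participants have not been through the T4 monitoring or the T5 week. This stands as a reason to keep the Visit 3 rating and not to merge it with earlier ones. It is not a reason to leave out the earlier ones. It is also true that Visit 2 alone recovers few people.

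**Conclusion.** The point holds in a limited form. The only listed self-report of study burden will come only from those who attend the one-month follow-up. At the plan's own retention benchmarks it will be missing for 12-20 of 80 participants (15-25%), including any who left because of burden, and nothing described in the plan would show why they left.

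The count rests on enrollment of 80, loss within the benchmark ranges, and retention standing for attendance. The size of any bias is unknown. It runs from 3-5 points under the assumed doubling to the full 15-25 point width of the bounds, and the document gives no rate that would narrow this.

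The gap affects one descriptive item within a primary-aim construct. It does not undermine the Aim 1 benchmarks. This is a cheap improvement, not a flaw that must be fixed before the trial can be interpreted.

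**What to change.** Give the existing Study Burden form at Visit 2 as well as Visit 3, the schedule already used for the Adverse Effects Survey. This adds about 4 respondents at the plan's benchmarks and takes a rating closer to the intervention-period survey load. Send the same form electronically to anyone who withdraws or misses a visit, since this is the only step that can reach the remaining 8-16.

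Report ratings separately for Visit 2, Visit 3 and exit. Give the number answering out of those enrolled in each arm, and best- and worst-case bounds for non-responders as in the working. Do not pool each person's last available rating, because that mixes ratings made after different amounts of exposure. State in the SAP whether the acceptability survey in the Overview is this form, and when it is given.

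The cost is one short existing form at an existing visit, an electronic version for leavers, and a few minutes per participant. Response from leavers will be incomplete, so the bounds will narrow but not close.
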